8.3 Subject Confidentiality

For the protection of personal data, AbbVie has developed a robust security program focused on due diligence in design, managed change, and information security governance. Information Security policies govern the Information Security functions including identity and access management, operations, infrastructure, application, and third-party security requirements. The risk-based AbbVie Data Classification Tool dictates the level of scrutiny and control required for the relevant activities per AbbVie's Information Security policies taking into account the sensitivity of the data.

Before subject's data is shared with AbbVie, the study investigator and staff will replace any information that could directly identify a subject (such as name, address, and contact information) with an assigned numerical study identifier or "code" which AbbVie cannot link to that subject's identity in order to protect the confidentiality of the data.

AbbVie has a data protection impact assessment program to ensure and document the appropriate controls and safeguards stated above are in place for clinical trial data that it controls and maintains and these processing activities respect privacy of clinical trial subjects. AbbVie also maintains robust security incident response policies and procedures, including requirements for the containment of any data related incidents, the mitigation measures where needed, and notification to authorities or affected individuals where required.

9 SOURCE DOCUMENTS AND CASE REPORT FORM COMPLETION

The investigator is responsible for ensuring the accuracy, completeness, legibility, and timeliness of the data reported. All source documents should be attributable, legible, contemporaneous, original, accurate, and complete to ensure accurate interpretation of data. Clinical site monitoring is conducted to ensure that the rights and well-being of human subjects are protected, that the reported trial data are accurate, complete, and verifiable, and that the conduct of the trial is in compliance with the currently approved protocol, ICH Good Clinical Practice (GCP), and applicable local regulatory requirement(s). During states of emergency or pandemic situations, remote data review/verification may be employed if allowed by the local regulatory authority, IRB/IEC, and the study site.

10 DATA QUALITY ASSURANCE

AbbVie will ensure that the clinical trial is conducted with a quality management system that will define quality tolerance limits in order to ensure human subject protection and reliability of study results. Data will be generated, documented, and reported in compliance with the protocol, ICH GCP, and applicable regulatory requirements.

11 START AND COMPLETION OF THE STUDY

The start-of-study is defined as the date of the first site activated.

The end-of-study is defined as the date of the last subject's last visit or the actual date of follow-up contact, whichever is later; and in the last country where the study was conducted.

APPENDIX A. STUDY-SPECIFIC ABBREVIATIONS AND TERMS

Abbreviation	Definition
6-MP	6-mercaptopurine
Ab	antibody
ACTH	adrenocorticotrophic hormone
ADA	anti-drug antibody
ADC	antibody-drug conjugate
AE	adverse event
ALC	absolute lymphocyte count
ALT	alanine aminotransferase
ANC	absolute neutrophil count
AP	abdominal pain
AST	aspartate aminotransferase
AZA	azathioprine
BCG	bacilli Calmette-Guérin
BL	Baseline
BMD	bone mineral density
BMI	body mass index
C diff	Clostridium difficile
CD	Crohn's Disease
CDAI	Crohn's Disease Activity Index
CI	confidence interval
CMH	Cochran-Mantel-Haenszel
CO ₂	carbon dioxide
COPD	chronic obstructive pulmonary disease
COVID-19	Coronavirus disease-2019
CR100	A decrease in CDAI ≥ 100 points from Baseline
CR70	A decrease in CDAI ≥ 70 points from Baseline
CTCAE	Common Terminology Criteria for Adverse Events
CTX	C-terminal telopeptide
CXR	chest x-ray
CYP3A	cytochrome P450 3A
DB	double-blind

Abbreviation	Definition
DMC	data monitoring committee
DNA	deoxyribonucleic acid
DSUR	Development Safety Update Report
DXA	dual-energy x-ray absorptiometry
E4W	every 4 weeks
ECG	electrocardiogram
eCRF	electronic case report form
EDC	electronic data capture
eGFR	Estimate glomerular filtration rate
EIM	extra intestinal manifestation
EOW	every other week
ePRO	electronic patient-reported outcome
FACIT-F	Functional Assessment of Chronic Illness Therapy-Fatigue
FCP	fecal calprotectin
FSH	follicle stimulating hormone
GCP	good clinical practice
GRM	glucocorticoid receptor modulator
HbA1c	Hemoglobin A1c
HBc	Hepatitis B core
HBc Ab	Hepatitis B core antibody
HBs	Hepatitis B surface
HBs Ab	Hepatitis B surface antibody
HBs Ag	hepatitis B surface antigen
HBV	hepatitis B virus
Hct	hematocrit
HCV	hepatitis C virus
HCV Ab	HCV antibody
HDL	high density lipoprotein
HIV	human immunodeficiency virus
HIV	human immunodeficiency virus
HPA	Hypothalamic-pituitary-adrenal axis
hs-CRP	high-sensitivity C-reactive protein

Abbreviation	Definition
IBDQ	Inflammatory Bowel Disease Questionnaire
ICH	International Council for Harmonisation
IEC	independent ethics committee
IgE	Immunoglobulin E
IgG	immunoglobulin G
IMP	Investigational Medicinal Product
IRB	institutional review board
IRT	Interactive response technology
ITT	Intent-to-treat
IU	International units
IUP	interim unblinding plan
IV	Intravenous (ly)
JAK	Janus kinase
LCMS	Liquid chromatography-mass spectrometry
LDL	low density lipoprotein
MACE	major adverse cardiac event
MCP-Mod	Multiple Comparison Procedure - Modeling
MedDRA	Medical Dictionary for Regulatory Activities
MMRM	Mixed Effect Model Repeated Measurements
mRNA	messenger RNA
MTX	methotrexate
N/A	not applicable
nAb	neutralizing antibody
NCI	National Cancer Institute
NMSC	nonmelanoma skin cancer
NRI-MI	Non-responder imputation incorporating multiple imputation
NSAID	nonsteroidal anti-inflammatory drug
OC	osteocalcin
P1NP	procollagen type 1 N-propeptide
PBMC	peripheral blood mononuclear cells
PCR	polymerase chain reaction
PD	pharmacodynamics

Abbreviation	Definition
PFS	pre-filled syringe
PGIC-CD+	Patient Global Impression of Change – Crohn's Disease+
PGIS-CD+	Patient Global Impression of Severity – Crohn's Disease+
PK	pharmacokinetic(s)
PPD	purified protein derivative
PPE	Personal Protective Equipment
PRO	Patient-reported outcome
PRO	patient-reported outcome
RNA	ribonucleic acid
RSI	reference safety information
SAE	serious adverse event
SAP	statistical analysis plan
SAR	serious adverse reaction
SARS-CoV-2	severe acute respiratory syndrome coronavirus 2
SC	subcutaneous
SES-CD	Simplified Endoscopic Score for CD
SF	stool frequency
SF-36	short form-36
SUSAR	suspected unexpected serious adverse reaction
TA MD	Therapeutic Area Medical Director
TB	tuberculosis
TEAE	treatment-emergent adverse event
TNF	tumor necrosis factor
TSH	thyroid stimulating hormone
ULN	upper limit of normal
Wk	week

APPENDIX D. ACTIVITY SCHEDULE

The following table shows the required activities across the 12-Week Induction Period, the 12-Week Re-Induction Period, and the 40-Week Maintenance Period subject encounters. The individual activities are described in detail in the **Operations Manual** ([Appendix F](#)). Allowed modifications due to state of emergency or pandemic situations are detailed in the Operations Manual.

Study Activities Table

12-Week Double-Blind Induction Period

Activity	Screening	Visit Induction Period (Week)						Premature Discontinuation	Follow-up 70-Day Visit	
		Baseline (Week 0, Day 1)	2	4	6	8	10			12
INTERVIEWS AND QUESTIONNAIRES										
Subject information and informed consent	✓									
Confirm Eligibility	✓	✓								
Medical/Surgical History including disease specific history	✓	✓								
Alcohol use	✓									
Nicotine usage	✓									
Adverse Event Assessment	✓	✓	✓	✓	✓	✓	✓	✓	✓	✓
Record prior and concomitant medication/therapy	✓	✓	✓	✓	✓	✓	✓	✓	✓	✓
TB risk assessment questionnaire	✓									
SF-36		✓		✓		✓		✓	✓	
IBDQ		✓		✓		✓		✓	✓	
FACIT-Fatigue		✓		✓		✓		✓	✓	
PGIC-CD+				✓		✓		✓	✓	
PGIS-CD+		✓		✓		✓		✓	✓	
CDAI Components (may be performed at additional visits not marked if needed to confirm eligibility for Rescue Therapy)		✓	✓	✓		✓		✓	✓	
Automatic calculation of CDAI in EDC (may be performed at additional visits not marked if needed to confirm eligibility for Rescue Therapy)		✓				✓		✓		
Bowel Incontinence Scale		✓		✓		✓		✓	✓	
Dispense Subject Diary	✓									

Activity	Screening	Visit Induction Period (Week)							Premature Discontinuation	Follow-up 70-Day Visit	
		Baseline (Week 0, Day 1)	2	4	6	8	10	12			
Subject Diary Review		✓	✓	✓	✓	✓	✓	✓	✓		
Dispense wearable device (substudy only)		✓	Subject wears device continuously and measures stool frequency.								
Collect wearable device (substudy only)								✓			
 LOCAL LABS AND EXAMS											
Height	✓										
Body Weight	✓	✓	✓	✓		✓		✓	✓	✓	
Vital Signs	✓	✓	✓	✓		✓		✓	✓	✓	
Complete Physical Exam	✓	✓						✓	✓		
Symptom Directed Physical Exam			✓	✓		✓					
12-Lead ECG	✓							✓	✓		
Endoscopy (may be performed at additional visits not marked if needed to confirm eligibility for Rescue Therapy)	✓							✓	✓		
Automatic calculation of SES-CD score and endoscopic response status in EDC								✓			
Intestinal Biopsies	✓							✓			
DXA scan	✓										
Chest x-ray	✓										
Blood sample for anti-adalimumab antibody assay (where mandated by local requirements)	✓										
Urine pregnancy test (females of childbearing potential)		✓		✓		✓		✓	✓	✓	
 CENTRAL LABS											
Serum pregnancy test (females of childbearing potential); FSH, if applicable	✓										
hs-CRP		✓	✓	✓		✓		✓	✓		

Activity	Screening	Visit Induction Period (Week)							Premature Discontinuation	Follow-up 70-Day Visit
		Baseline (Week 0, Day 1)	2	4	6	8	10	12		
FCP		✓		✓				✓	✓	
Clostridium difficile test	✓									
Hematology	✓	✓	✓	✓		✓		✓	✓	✓
HbA1c	✓							✓		✓
Clinical Chemistry	✓	✓	✓	✓		✓		✓	✓	✓
Urinalysis	✓	✓		✓		✓		✓	✓	
Lipid Panel		✓						✓		
TSH	✓									
TB testing (QuantiFERON-TB Gold test and/or local PPD skin test)	✓									
HIV Test	✓									
HBV Test	✓							✓ if required by local regulations		
HCV Test	✓									
Beta-D-glucan (central or local lab; Japan only)	✓									
Blood samples for conjugated ADC (serum), total antibody (serum), free A-167770 (plasma) assays		✓	✓	✓		✓		✓	✓	✓
Blood samples for ADA Assay including serum ADA titer and nAb assays		✓		✓		✓		✓	✓	✓
Blood sample for bone biomarkers P1NP, OC and CTX		✓	✓	✓		✓		✓		
Blood sample for free and total cortisol (serum)		✓	✓	✓		✓		✓	✓	✓
Blood sample for ACTH		✓	✓	✓		✓		✓	✓	✓
Optional Biomarker sample: Plasma/serum proteomic		✓	✓			✓		✓		
Optional biomarker sample: PBMC		✓	✓			✓		✓		
Optional biomarker sample: RNA		✓	✓			✓		✓		

Activity	Screening	Visit Induction Period (Week)							Premature Discontinuation	Follow-up 70-Day Visit
		Baseline (Week 0, Day 1)	2	4	6	8	10	12		
Optional biomarker sample: DNA		✓	✓			✓		✓		
Rx TREATMENT										
Assign Study Drug		✓								
Dispense Study Drug		✓	✓	✓	✓	✓	✓			
Administer Study Drug		✓	✓	✓	✓	✓	✓			
Inadequate response assessment to determine eligibility for rescue therapy (may be performed at additional visits not marked if needed to confirm eligibility for Rescue Therapy)						✓		✓		
Automatic determination of eligibility for the Maintenance Period in EDC								✓		

ACTH = adrenocorticotrophic hormone; ADA = anti-drug antibody; ADC = antibody-drug conjugate; CDAI = Crohn's Disease Activity Index; CTX = C-terminal telopeptide of type 1 collagen; DNA = deoxyribonucleic acid; DXA = dual-energy X-ray absorptiometry; ECG = electrocardiogram; EDC = electronic data capture; FACIT-Fatigue = Functional Assessment of Chronic Illness Therapy-Fatigue; FCP = Fecal calprotectin; FSH = follicle stimulating hormone; HbA1c = Hemoglobin A1c; HBV = hepatitis b virus; HCV = hepatitis C virus; HIV = human immunodeficiency virus; hs-CRP = high sensitivity C-reactive protein; IBDQ = Inflammatory Bowel Disease Questionnaire; nAb = neutralizing antibody; OC = osteocalcin; P1NP = procollagen type I N-propeptide; PBMC = peripheral blood mononuclear cells; PGIC-CD+ = Patient Global Impression of Change – Crohn's Disease+; PGIS-CD+ = Patient Global Impression of Severity – Crohn's Disease+; PPD = purified protein derivative; RNA = ribonucleic acid; SF-36 = Short Form-36; TB = tuberculosis; TSH = thyroid stimulating hormone

12-Week Double-Blind Re-Induction Period

Activity	Visit Re-Induction (Week)							Premature Discontinuation	Follow-up 70-Day Visit
	Baseline (Week 0, Day 1)	2	4	6	8	10	12		
INTERVIEWS AND QUESTIONNAIRES									
Adverse Event Assessment		✓	✓	✓	✓	✓	✓	✓	✓
Record prior and concomitant medication/therapy		✓	✓	✓	✓	✓	✓	✓	✓
SF-36							✓	✓	
IBDQ							✓	✓	
FACIT-Fatigue							✓	✓	
PGIC-CD+							✓	✓	
PGIS-CD+							✓	✓	
CDAI Components		✓	✓		✓		✓	✓	
Automatic calculation of CDAI in EDC							✓		
Bowel Incontinence Scale							✓	✓	
Subject Diary Review		✓	✓	✓	✓	✓	✓	✓	
LOCAL LABS AND EXAMS									
Body Weight		✓	✓		✓		✓	✓	✓
Vital Signs		✓	✓		✓		✓	✓	✓
Complete Physical Exam							✓	✓	
Symptom Directed Physical Exam		✓	✓		✓				
12-Lead ECG							✓	✓	
Endoscopy							✓	✓	
Automatic calculation of SES-CD score and endoscopic response status in EDC							✓		
Intestinal biopsies							✓		

Activity	Visit Re-Induction (Week)							Premature Discontinuation	Follow-up 70-Day Visit
	Baseline (Week 0, Day 1)	2	4	6	8	10	12		
LOCAL LABS AND EXAMS									
Urine pregnancy test (females of childbearing potential)			✓		✓		✓	✓	✓
CENTRAL LABS									
hs-CRP		✓	✓		✓		✓	✓	
FCP							✓	✓	
Hematology		✓	✓		✓		✓	✓	✓
HbA1c							✓		✓
Clinical Chemistry		✓	✓		✓		✓	✓	✓
Urinalysis			✓		✓		✓	✓	
Lipid Panel							✓		
HBV test (if required by local regulations)							✓		
Blood samples for conjugated ADC (serum), total antibody (serum), free A-1677770 (plasma) assays							✓	✓	✓
Blood samples for ADA Assay (serum) including ADA titer and nAb assays (Central Lab shipping and lab handling)							✓	✓	✓
Blood sample for bone biomarkers P1NP, OC and CTX			✓				✓		
Blood sample for free and total cortisol (serum)			✓		✓		✓	✓	✓
Blood sample for ACTH			✓		✓		✓	✓	✓
Optional Biomarker sample: Whole Blood Plasma/serum proteomic			✓				✓		
Optional biomarker sample: Whole Blood Peripheral Blood Mononuclear Cells			✓				✓		

Activity	Visit Re-Induction (Week)							Premature Discontinuation	Follow-up 70-Day Visit
	Baseline (Week 0, Day 1)	2	4	6	8	10	12		
Optional biomarker sample: Whole Blood RNA			✓				✓		
Optional biomarker sample: Whole Blood DNA			✓				✓		
Rx TREATMENT									
Assign Study Drug	✓								
Administer Study Drug	✓	✓	✓	✓	✓	✓			
Dispense Study Drug	✓	✓	✓	✓	✓	✓			
Automatic determination of eligibility for the Maintenance Period in EDC							✓		

ACTH = adrenocorticotrophic hormone; ADA = anti-drug antibody; ADC = antibody-drug conjugate; CDAI = Crohn's Disease Activity Index; CTX = C-terminal telopeptide of type 1 collagen; DNA = deoxyribonucleic acid; ECG = electrocardiogram; EDC = electronic data capture; FACIT-Fatigue = Functional Assessment of Chronic Illness Therapy-Fatigue; FCP = Fecal calprotectin; HbA1c = Hemoglobin A1c; HBV = hepatitis b virus; HCV = hepatitis C virus; hs-CRP = high sensitivity C-reactive protein; IBDQ = Inflammatory Bowel Disease Questionnaire; nAb = neutralizing antibody; OC = osteocalcin; P1NP = procollagen type I N-propeptide; PGIC-CD+ = Patient Global Impression of Change – Crohn's Disease+; PGIS-CD+ = Patient Global Impression of Severity – Crohn's Disease+; RNA = ribonucleic acid; SF-36 = Short Form-36

40-Week Maintenance Period

Activity	Baseline (Week 0, Day 1)	Maintenance Period (Week)																			Premature Discontinuation	Follow-up 70- Day Visit
		2	4	6	8	10	12	14	16	18	20	22	24	26	28	30	32	34	36	38		
INTERVIEWS AND QUESTIONNAIRES																						
Adverse Event Assessment		✓	✓	✓	✓	✓	✓	✓	✓	✓	✓	✓	✓	✓	✓	✓	✓	✓	✓	✓	✓	
Record concomitant medication/therapy		✓	✓	✓	✓	✓	✓	✓	✓	✓	✓	✓	✓	✓	✓	✓	✓	✓	✓	✓	✓	
TB risk assessment questionnaire																				✓		
SF-36				✓				✓				✓				✓				✓	✓	
IBDQ				✓				✓				✓				✓				✓	✓	
FACIT-Fatigue				✓				✓				✓				✓				✓	✓	
PGIC-CD+				✓				✓				✓				✓				✓	✓	
PGIS-CD+				✓				✓				✓				✓				✓	✓	
CDAI Components (may be performed at additional visits not marked if needed to confirm eligibility for Rescue Therapy)				✓				✓				✓				✓				✓	✓	
Automatic calculation of CDAI in EDC (may be performed at additional visits not marked if needed to confirm eligibility for Rescue Therapy)				✓				✓				✓				✓						
Bowel Incontinence Scale				✓				✓				✓				✓				✓	✓	
Subject Diary Review		✓	✓	✓	✓	✓	✓	✓	✓	✓	✓	✓	✓	✓	✓	✓	✓	✓	✓	✓	✓	
LOCAL LABS AND EXAMS																						
Weight				✓				✓				✓				✓				✓	✓	
Vital Signs		✓		✓				✓				✓				✓				✓	✓	

Activity	Baseline (Week 0, Day 1)	Maintenance Period (Week)																		Premature Discontinuation	Follow-up 70- Day Visit				
		2	4	6	8	10	12	14	16	18	20	22	24	26	28	30	32	34	36			38	40		
Complete Physical Exam													✓									✓	✓		
Symptom Directed Physical Exam					✓						✓										✓				
12-Lead ECG											✓												✓	✓	
Endoscopy (may be performed at additional visits not marked if needed to confirm eligibility for Rescue Therapy)																							✓	✓	
Intestinal Biopsies																							✓		
DXA scan																							✓		
Urine (U) pregnancy test (females of childbearing potential)			✓		✓		✓		✓		✓		✓		✓		✓		✓		✓		✓	✓	✓
Chest x-ray (subjects with a newly positive PPD and/or QuantiFERON-TB Gold Plus test after Baseline or a positive response to TB risk questionnaire, Part I questions)																							✓		
CENTRAL LABS																									
hs-CRP					✓					✓					✓						✓		✓	✓	
FCP					✓					✓					✓						✓		✓	✓	
Hematology		✓			✓					✓					✓						✓		✓	✓	✓
HbA1c										✓											✓		✓	✓	✓
Clinical Chemistry		✓			✓					✓					✓						✓		✓	✓	✓
Urinalysis		✓			✓					✓					✓						✓		✓	✓	
Lipid Panel										✓					✓						✓		✓		
TB testing (QuantiFERON-TB Gold test and/or local PPD skin test)																							✓		

Activity	Baseline (Week 0, Day 1)	Maintenance Period (Week)																		Premature Discontinuation	Follow-up 70- Day Visit				
		2	4	6	8	10	12	14	16	18	20	22	24	26	28	30	32	34	36			38	40		
HBV test (if required due to local regulations)							✓					✓						✓							
Blood samples for conjugated ADC (serum), total antibody (serum), free A-167770 (plasma) assays					✓				✓			✓					✓				✓		✓	✓	
Blood samples for ADA Assay (serum) including ADA titer and nAb assays (Central Lab shipping and lab handling)					✓				✓			✓					✓				✓		✓	✓	
Blood sample for bone biomarkers P1NP, OC and CTX												✓									✓				
Blood sample for free and total cortisol (serum)		✓			✓				✓			✓					✓				✓		✓	✓	
Blood sample for ACTH		✓			✓				✓			✓					✓				✓		✓	✓	
Optional Biomarker sample: Whole Blood Plasma/serum proteomic												✓									✓				
Optional biomarker sample: Whole Blood PBMC												✓									✓				
Optional biomarker sample: Whole Blood RNA												✓									✓				
Optional biomarker sample: Whole Blood DNA												✓									✓				
R_x TREATMENT																									
Inadequate response assessment to determine eligibility for Rescue Therapy (may be performed at additional visits not marked if needed to confirm eligibility for Rescue Therapy)					✓				✓			✓					✓				✓				

Activity	Baseline (Week 0, Day 1)	Maintenance Period (Week)																		Premature Discontinuation	Follow-up 70- Day Visit		
		2	4	6	8	10	12	14	16	18	20	22	24	26	28	30	32	34	36			38	40
Assign Study Drug	✓																						
Administer Study Drug	✓	✓	✓	✓	✓	✓	✓	✓	✓	✓	✓	✓	✓	✓	✓	✓	✓	✓	✓	✓	✓		
Dispense Study Drug	✓	✓	✓	✓	✓	✓	✓	✓	✓	✓	✓	✓	✓	✓	✓	✓	✓	✓	✓	✓	✓		

ACTH = adrenocorticotrophic hormone; ADA = anti-drug antibody; ADC = antibody-drug conjugate; CDAI = Crohn's Disease Activity Index; CTX = C-terminal telopeptide of type 1 collagen; DNA = deoxyribonucleic acid; DXA = dual-energy X-ray absorptiometry; ECG = electrocardiogram; EDC = electronic data capture; FACIT-Fatigue = Functional Assessment of Chronic Illness Therapy-Fatigue; FCP = Fecal calprotectin; HbA1c = Hemoglobin A1c; HBV = hepatitis B virus; HCV = hepatitis C virus; HIV = human immunodeficiency virus; hs-CRP = high sensitivity C-reactive protein; IBDQ = Inflammatory Bowel Disease Questionnaire; nAb = neutralizing antibody; OC = osteocalcin; P1NP = procollagen type I N-propeptide; PBMC = peripheral blood mononuclear cells; PGIC-CD+ = Patient Global Impression of Change – Crohn's Disease+; PGIS-CD+ = Patient Global Impression of Severity – Crohn's Disease+; PPD = purified protein derivative; RNA = ribonucleic acid; SF-36 = Short Form-36; TB = tuberculosis

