--	--

Key Eligibility Criteria:	
Male or female between 18 and 75 years of age inclusive at the time of Screening.
 
Confirmed diagnosis of CD for at least 3 months prior to Baseline of the Induction Period.
 
CDAI score 220 to 450 at Baseline of the Induction Period.
 
Endoscopic evidence of mucosal inflammation as documented by an SES-CD of ≥ 6 for ileocolonic or colonic disease or SES-CD of ≥ 4 for isolated ileal disease as scored by a central reader. All eligible scores must exclude the presence of narrowing component.
 
Demonstrated intolerance or inadequate response to one or more of the following biologic agents: infliximab, adalimumab, certolizumab pegol, vedolizumab, natalizumab, ustekinumab, or risankizumab. Subjects with prior intolerance to adalimumab are not eligible to enroll.

Study Drug and Duration of Treatment:	
Screening up to 35 days (minimum of 8 days).
 
Overall maximum individual treatment duration is planned for up to 448 days (~64 weeks) with the following:
 
 • Double-Blind Induction Period for 12 weeks with placebo or ABBV-154: Induction Group 1) loading dose of 150 mg IV at Week 0, followed by 80 mg SC at Week 2 and EOW; Induction Group 2) loading dose of 300 mg IV at Week 0, followed by 230 mg SC at Week 2 and EOW; Induction Group 3) loading dose of 600 mg IV at Week 0, followed by 530 mg SC at Week 2 and EOW; Induction Group 4) loading dose of 600 mg IV at Week 0, followed by 530 mg SC at Weeks 4 and 8, and placebo at Weeks 2, 6, and 10; and Induction Group 5) matching placebo. • Double-Blind Re-Induction Period for 12 weeks in subjects who are considered as clinical non-responders and endoscopic non-responders at Week 12 of the Induction Period: Re-Induction Group 1) ABBV-154 300 mg IV at Week 0 of the Re-Induction Period, followed by 230 mg SC at Week 2 and EOW or Re-Induction Group 2) ABBV-154 600 mg IV at Week 0 of the Re-Induction Period, followed by 530 mg SC at Week 2 and EOW; • Double-Blind Maintenance Period for 40 weeks with placebo or ABBV-154 80 mg SC EOW or 230 mg SC EOW; 
Follow-up Period of 70 days after last study drug administration.

Date of Protocol Synopsis:	
20 December 2022

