- Change from Baseline in daily physical activity for subjects participating in the Wearable Device Substudy.
- Change from Baseline in sleep parameters for subjects participating in the Wearable Device Substudy.
- Change from Baseline in stool frequency, as captured from the wearable device, for subjects participating in the Wearable Device Substudy.
- Patient Global Impression of Change – Crohn's Disease+ (PGIC-CD+).
- Change from Baseline in Patient Global Impression of Severity – Crohn's Disease+ (PGIS-CD+).
- Achievement of absence of bowel urgency.
- Change from Baseline in average daily bowel urgency frequency.
- Achievement of absence of rectal bleeding.

All endoscopic endpoints will be scored by a central reviewer.

SF/AP-based efficacy endpoints will be analyzed in the subset of subjects with an average daily liquid or very soft SF score ≥ 4 and/or average daily AP score ≥ 2 at Baseline.

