The Primary Analysis for the Induction Period and Re-Induction Period will be performed after all subjects have either completed Week 12 of the Induction Period and Re-Induction Period, respectively, or prematurely discontinued study participation. The final analysis will be conducted after all subjects have completed Week 40 of the Maintenance Period plus the 70-day Follow-up Visit or prematurely discontinued study participation. To ensure the integrity of the trial, the study sites and subjects will remain blinded until the final database lock is completed (see Section 7.1).

Interim analyses may be performed as outlined in Section 7.8.

The Wearable Device Substudy will enroll up to approximately 75 subjects in countries and sites where the digital health technology device is deployed and available. For subjects participating in the substudy, data for sleep parameters, daily physical activity, and stool frequency will be collected continuously throughout the Induction Period.

The schematic of the study is shown in [Figure 1](#). Further details regarding study procedures are located in the Operations Manual. See [Section 5.1](#) for information regarding eligibility criteria.

Figure 1. Study Schematic

DB = double-blind; EOW = every other week; IV = intravenous; SC = subcutaneous; Wk = week

* Responders are defined as clinical responders AND/OR endoscopic responders (per local read), and non-responders are defined as clinical non-responders AND endoscopic non-responders (per local read). Clinical responder is defined at Week 12 of the Induction Period or Re-Induction Period as a decrease in CDAI \geq 100 points from Baseline (CR100). Endoscopic responder is defined at Week 12 of the Induction Period or Re-Induction Period as a decrease in SES-CD $>$ 50% from Baseline (or for subjects with isolated ileal disease and a Baseline SES-CD of 4, at least a 2-point reduction from Baseline) (per local read). In the case of missing data where clinical response and endoscopic response cannot be calculated, subjects will be considered as non-responders for the re-randomization criteria evaluation.

** Only subjects who are considered to be clinical non-responders and endoscopic non-responders (per local read) at Week 12 of the Induction Period will be re-randomized into the Re-Induction Period.

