9.0 Efficacy Analyses

9.1 General Considerations

All efficacy analyses will be conducted in the ITT Populations in each period. All tests will be 2-sided at an alpha level of 0.1.

For all efficacy endpoints, the descriptive statistics will be provided by treatment group for each of the study period. The statistics include number of observations, mean, standard deviation, 95% CI, minimum, median, and maximum for continuous variables, and number, percent and two-sided 95% CI for discrete variables. And number of subjects with missing data due to COVID-19 pandemic will be summarized for primary and secondary efficacy endpoints.

Unless otherwise specified, any subject will be analyzed according to the actual stratum the subject belongs to.

The Primary Analysis for the Induction Period and Re-Induction Period will be performed after all subjects have completed Week 12 of the Induction Period and Re-Induction Period, respectively, or prematurely discontinued study participation. This is the final efficacy analysis for the Induction Period and Re-Induction Period, respectively.

The final analysis will be conducted after all subjects have completed Week 40 of the Maintenance Period plus the 70 day Follow-up Visit or prematurely discontinued study participation. This is the final efficacy analysis for the Maintenance Period. To ensure the

integrity of the trial, the study sites and subjects will remain blinded until the final database lock is completed.

In Section 9.0, "Baseline" refers to the last non-missing observation prior to the first administration of study drug in the Induction Period, unless specified otherwise. "Comparison of treatment groups" refers to (i) comparison of each ABBV-154 group and placebo group in the Induction Period; (ii) comparison of Re-Induction Group 2 and Re-Induction Group 1 in the Re-Induction Period; (iii) comparison of each ABBV-154 group and placebo group for the randomized portion in the Maintenance Period.

"Stratification factors for the corresponding period" refers to randomization stratification factors specified in Section 2.3 except for the Maintenance Period, the randomization stratification factors used in efficacy analyses for the Maintenance Period are

- Achievement of CR100 at entry of the Maintenance Period (Week 12 of the Induction/Re-Induction Period): Yes vs No;
- Entry to the Maintenance Period: Induction Period vs Re-Induction Period.

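### The wearable device is first dispensed on the day of the IV loading dose, so three exploratory change-from-Baseline endpoints have no full pre-dose day or night of data

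*Protocol*

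**What the plan says.** Protocol Section 3.4 (Additional Efficacy Endpoints) contains three device endpoints. One is "Change from Baseline in daily physical activity for subjects participating in the Wearable Device Substudy"; the other two take the same form, one for sleep and one for stool frequency as the device records it. The same section sets Baseline at Week 0, Day 1 of the Induction Period and does not say that the value must be pre-dose.

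The Induction table in Appendix D has the row "Dispense wearable device (substudy only"), ticked at Baseline and blank at Screening. After that tick the row reads "Subject wears device continuously and measures stool frequency", and the device is collected at Week 12. Section 4.1 agrees: "data for sleep parameters, daily physical activity, and stool frequency will be collected continuously throughout the Induction Period".

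Study drug is administered at that same Baseline visit. Every active induction regimen starts with an IV loading dose at Week 0 (Section 4.1), and Section 5.7 prefers dosing between 7 and 11 am. The subject diary, by contrast, is dispensed at Screening. The Synopsis gives the length of that period as "Screening up to 35 days (minimum of 8 days").

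SAP Section 1.0 leaves the wearable data to a separate analysis.

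**The concern.** A change-from-Baseline endpoint normally contrasts on-treatment values with values recorded before treatment. Here the device and the first dose arrive at the same visit. If the first days of wear serve as the reference, the ABBV-154 arms have some drug effect inside the reference and the placebo arm has none. Subtracting that reference removes part of the treatment effect and pulls the difference in change towards zero.

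A pre-dose device measurement is also lost as a covariate, in a substudy of up to about 75 subjects. Device and diary stool frequency share no pre-treatment window in which they could be compared. Section 4.2 says the device is being evaluated to inform later studies, so a diluted contrast could make it look less responsive than it is.

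**Working it through.** The plan states no figure for this substudy, so there is nothing to reproduce. The check has two parts.

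**1. Pre-dose wear under the schedule**

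| Item | Source | Timing |
|---|---|---|
| Device dispensed | Protocol Appendix D, Induction table | Baseline (Week 0, Day 1) only |
| Study drug first given | Protocol Appendix D; Section 4.1 | Baseline (Week 0, Day 1) |
| Preferred time of dosing | Protocol Section 5.7 | 7 to 11 am |
| Device data collected | Protocol Section 4.1; Synopsis | Induction Period only, 12 × 7 = 84 days |
| Subject diary dispensed | Protocol Appendix D | Screening |

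Full pre-dose days of activity or stool counts: 0. Pre-dose nights of sleep: 0. At most, some hours on Day 1 precede the infusion. The diary has a pre-dose window because it is handed out earlier.

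**2. Size of the dilution**

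Suppose the drug effect builds exponentially with half-time h weeks, so that the fraction reached at week t is 1 − exp(−kt), with k = ln 2 / h. Let the reference be the mean over the first w weeks after dosing. The share of the Week 12 between-group difference in change that is lost is

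g = [1 − (1 − exp(−kw)) / (kw)] / [1 − exp(−12k)].

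Both h and w are assumptions; the documents give neither.

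Seven-day window (w = 1):
- h = 1: k = 0.693; numerator 1 − 0.500/0.693 = 0.279; denominator 1.000; g ≈ 28%.
- h = 2: k = 0.347; numerator 1 − 0.293/0.347 = 0.155; denominator 0.984; g ≈ 16%.
- h = 4: k = 0.173; numerator 1 − 0.159/0.173 = 0.082; denominator 0.875; g ≈ 9%.

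One-day window (w = 1/7), same formula:
- h = 1: g ≈ 4.8%.
- h = 2: g ≈ 2.5%.
- h = 4: g ≈ 1.4%.

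The direction does not depend on h or w: any beneficial effect inside the window reduces the difference in change. A one-day reference has little bias, but it is a noisier baseline than a mean of several days.

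At about 75 subjects in five groups, there would be 75/5 = 15 per group if the substudy were spread evenly, which the protocol does not promise.

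**The case against.** **The endpoints can still be computed.** A reader might infer that the substudy cannot measure what it lists. The documents do not support that. Section 3.4 defines Baseline as Week 0, Day 1 without requiring it to be pre-dose, so a Day 1 or early-wear reference can be formed and change from it calculated. Because the arms are randomized, on-treatment levels can also be compared without any baseline. The measure is diluted, not lost.

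**The larger dilution figures need a window the plan never states.** This stands. The 9 to 28% range assumes a 7-day post-dose reference; a one-day reference gives 1 to 5%. Nor do the documents support fast onset: the rationale for the loading dose in Section 4.2 concerns drug levels, not how quickly sleep, activity or stool frequency change.

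**The SAP's pre-dose definition might seem to be breached.** SAP Section 9.1 takes Baseline as the "last non-missing observation prior to the first administration of study drug in the Induction Period". That definition applies to the analyses in SAP Section 9.0, and SAP Section 1.0 places the wearable data outside the SAP. It does not govern these endpoints.

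**Other documents may define a window.** The Operations Manual and the separate wearable analysis are not among the documents reviewed, and either may specify a reference period. Neither could supply full pre-dose days or nights, however, from a device first dispensed on dosing day and without contradicting Appendix D.

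**Other covariates and low stakes.** Diary stool frequency, CDAI and FACIT-F at Baseline remain available for adjustment, so precision is not wholly forfeited; what is missing is a pre-dose value of the device measures themselves. The endpoints are exploratory, and the substudy is small.

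**Conclusion.** The point holds as a limited design weakness. On the schedule as written, the three wearable change-from-Baseline endpoints have no full pre-dose day or night of data, and any reference value is essentially post-dose. The resulting shrinkage of the between-group difference in change is about 1 to 5% for a one-day window and about 9 to 28% for a 7-day window. Both ranges rest on assumed exponential onset with half-times of 4 to 1 weeks.

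The consequence is confined to exploratory substudy endpoints. Randomized comparison of on-treatment levels remains valid. The finding about the schedule is firm; the size of the dilution is only illustrative. Acting on it is a cheap improvement, and worthwhile because pre-dose wear cannot be recovered after Day 1.

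**What to change.** - **Appendix D:** move the device-dispensing tick from Baseline to Screening, alongside the subject diary. The substudy exclusions in eligibility criterion 15 (sleep-disorder history, current sleep medication) can be judged then.
- **Synopsis and Section 4.1:** extend device data collection to start before Day 1 and run through Week 12.
- **Section 3.4 and the separate wearable analysis plan:** define wearable Baseline as the mean of the available valid days before the first dose, using up to the last 7, with a minimum such as 4, and excluding days around endoscopy as the diary rule in SAP Appendix B does.

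The flexible day count is needed because Screening can be as short as 8 days and includes endoscopy. The diary rule sets 4 days around endoscopy to missing; if all 4 fell within an 8-day Screening, 8 − 4 = 4 days would remain. Seven valid days are therefore not guaranteed without a longer Screening, but a minimum of 4 is workable and matches the diary's own minimum.

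The cost is some devices issued to subjects who then fail screening, including those found ineligible on CDAI at Baseline. No extra visit is needed. If dispensing cannot be moved, the wearable analysis plan should at least state the reference window, acknowledge that it is post-dose, and include the comparison of on-treatment levels.
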